10.0 ADVERSE EVENT REPORTING

10.1 Monitoring, recording and reporting adverse events

Adverse Event (AE) is any untoward medical occurrence that may present during treatment with a pharmaceutical product but which does not necessarily have a causal relationship with this treatment.

Adverse drug reaction is a response to a drug which is noxious and unintended and which occurs at doses normally used in man for prophylaxis, diagnosis, or therapy of disease or for the modification of physiologic function.

Assessing causal connections between agents and disease is fundamental to the understanding of adverse drug reactions. In general, a drug may be considered a contributory cause of an adverse event if, had the drug not been administered, 1) the event would not have happened at all, 2) the event would have occurred later than it actually did, or 3) the event would have been less severe.

All subjects will be monitored for AEs during the study. AEs will be recorded in the subject's source documents from the first dose through 30 days after the last dose. All Grade 1-4 AEs possibly, probably, likely related to study drug(s) will be captured within the eCRF. Grade 3 and 4 AEs will be captured irrespective of relatedness to study drug(s).

Hematologic lab abnormalities will not be recorded or reported as adverse except for prolonged myelosuppression as defined by the NCI-CTCAE criteria specific for leukemia, e.g. marrow hypocellularity on day 42 or later (6 weeks) from start of therapy without evidence of leukemia (< 5% blasts), or that results in dose modifications, interruptions or meets the protocol definition of DLT or SAE.

Serious Adverse Events (SAEs) will be captured starting from the date of consent. The Investigator or physician designee is responsible for verifying and providing source documentation for all adverse events and assigning the attribution for each event for all subjects enrolled on the trial. The Principal Investigator will sign and date the AE log per each patient at the completion of each course. Following signature, the AE log will be used as source documentation for the adverse events for attribution.

The Leukemia-specific Adverse Event Recording and Reporting Guidelines will be followed for the recording and reporting of adverse and serious adverse events.

1. Baseline events will be recorded in the medical history section of the case report form and will include the terminology event name, grade,

and start date of the event. The medical history section of the case report form will serve as the source document for baseline events once signed and dated by the principal investigator.

- a. Baseline events are any medical condition, symptom, or clinically significant lab abnormality present before the informed consent is signed
 - i. Hematologic laboratory abnormalities will not be recorded as baseline events for patients with acute leukemia, myelodysplastic syndrome, chronic lymphocytic leukemia, or chronic myeloid leukemia in blast phase.
 - ii. If exact start date is unknown, month and year or year may be used as the start date of the baseline event.
2. The maximum grade of the adverse event will be captured per course or protocol defined visit date.
3. These adverse events will be recorded in the case report form:
 - a. Any grade adverse event that is possibly, probably, or definitely related to the study drug(s).
 - b. All serious adverse events regardless of attribution to the study drug(s).
 - c. Any grade adverse event regardless of attribution to the study drug(s) that results in any dose modification.
4. Hematologic adverse events will not be recorded or reported for studies in patients with acute leukemia, myelodysplastic syndrome, chronic lymphocytic leukemia, or chronic myeloid leukemia in blast phase except for:
 - a. Prolonged myelosuppression as defined by the NCI-CTCAE criteria specific for leukemia, e.g. marrow hypocellularity on day 42 or later (6 weeks) from start of therapy without evidence of leukemia (< 5% blasts), or that results in dose modifications, interruptions or meets the protocol definition of DLT or SAE.
5. Serious adverse events will be reported according to institutional policy.
6. Protocol specific language regarding the recording and reporting of adverse and serious adverse events will be followed in the event of discordance between the protocol and Leukemia-specific adverse event recording and reporting guidelines.

10.2 Serious Adverse Events (SAEs)

An adverse event or suspected adverse reaction is considered “serious” if, in the view of either the investigator or the sponsor, it results in any of the following outcomes:

- Death
- A life-threatening adverse drug experience – any adverse experience that places the patient, in the view of the initial reporter, at immediate risk of death from the adverse experience as it occurred. It does not include an adverse experience that, had it occurred in a more severe form, might have caused death.

- Inpatient hospitalization or prolongation of existing hospitalization
- A persistent or significant incapacity or substantial disruption of the ability to conduct normal life functions.
- A congenital anomaly/birth defect.

Important medical events that may not result in death, be life-threatening, or require hospitalization may be considered a serious adverse drug experience when, based upon appropriate medical judgment, they may jeopardize the patient or subject and may require medical or surgical intervention to prevent one of the outcomes listed in this definition. Examples of such medical events include allergic bronchospasm requiring intensive treatment in an emergency room or at home, blood dyscrasias or convulsions that do not result in inpatient hospitalization, or the development of drug dependency or drug abuse (21 CFR 312.32).

- Important medical events as defined above, may also be considered serious adverse events. Any important medical event can and should be reported as an SAE if deemed appropriate by the Principal Investigator or the IND Office.

10.3 Reporting SAEs to the IND Office and MDACC IRB

- All events occurring during the conduct of a protocol and meeting the definition of a SAE must be reported to the IRB in accordance with the timeframes and procedures outlined in “The University of Texas M. D. Anderson Cancer Center Institutional Review Board Policy for Investigators on Reporting Unanticipated Adverse Events for Drugs and Devices”. Unless stated otherwise in the protocol, all SAEs, expected or unexpected, must be reported to the IND Office, regardless of attribution (within 5 working days of knowledge of the event).
- All life-threatening or fatal events, that are unexpected, and related to the study drug, must have a written report submitted within 24 hours (next working day) of knowledge of the event to the Safety Project Manager in the IND Office.
- Unless otherwise noted, the electronic SAE application (eSAE) will be utilized for safety reporting to the IND Office and MDACC IRB.
- Serious adverse events will be captured from the time of the first protocol-specific intervention, until 30 days after the last dose of drug, unless the participant withdraws consent. Serious adverse events must be followed until clinical recovery is complete and laboratory tests have returned to baseline, progression of the event has stabilized, or there has been acceptable resolution of the event.
- Additionally, any serious adverse events that occur after the 30

day time period that are related to the study treatment must be reported to the IND Office. This may include the development of a secondary malignancy.

10.4 Reporting SAEs to FDA:

- Serious adverse events will be forwarded to FDA by the IND Sponsor (Safety Project Manager IND Office) according to 21 CFR 312.32.

It is the responsibility of the PI and the research teams to ensure serious adverse events are reported according to the Code of Federal Regulations, Good Clinical Practices, the protocol guidelines, the IND Office guidelines, and Institutional Review Board policy

10.5 Investigator Communications with Pfizer

All Serious Adverse Events must be reported to Pfizer Clinical Trial Department utilizing the provided Pfizer SAE form.

- All SAEs, whether related or unrelated to study drugs and all pregnancies must be reported to Pfizer (by the investigator or designee) within 24 hours.
- All SAEs should be reported via confirmed facsimile (fax) transmission, or scanned and reported via electronic mail to:

SAE Email Address: [contact]

SAE [contact]

11.0 STATISTICAL CONSIDERATIONS

This is an open-label Phase IB/II multi-arm study. The primary objectives are to determine the maximum tolerable dose (MTD) and identify the dose of PF-04518600 (Arm A), and to evaluate the composite complete response (CRc) within 3 months of therapy initiation of the combination therapies: Azacitidine + venetoclax + GO (arm B), Azacitidine + avelumab + GO (arm C), Azacitidine + venetoclax + avelumab (arm D), Azacitidine + avelumab + PF-04518600 (arm E), and GO + glasdegib (arm F), in patients with relapsed/refractory AML. A total of up to 87 patients will be enrolled in the study (arms with up to 24 patients per arm in arms C-D and 30 patients in arm B, in addition to the 4 patients enrolled in arm A and 5 patients enrolled in arm F at the time of closing these two arms).

Dose safety evaluation for Arm A (PF-04518600 alone in RR AML):

The 0.3 mg/kg dose of PF-04518600 will be evaluated as this was the dose selected to move forward from the solid tumor PF-04518600 single agent dose finding study (B0601002, ClinicalTrials.gov NCT02315066). Up to four patients will be enrolled at the dose level of 0.3mg/kg of PF-04518600. This arm will be closed at this time to further enrollment due to lack of clinical efficacy and competing options of higher priority at our institution.

Lead-in safety evaluation for Arm B-F

A lead-in safety evaluation for Arm B-F will be conducted to confirm the safety and tolerability of the treatment combination. Up to 30 patients in arm B, 24 patients in arms C-D and up to 21 patients in arms E-F will be enrolled. Enrollment must be halted while the first 6 patients in each treatment arm are evaluated for safety (i.e. after all patients have received 2 cycles of therapy, or been followed for at least 56 days from the start of treatment).

The treatment combination will be considered as safe and continue to enroll a total of 30 patients (arm B) or 24 patients (arms C-D) or 15 patients (arms E-F) when there are no more than 1 out of 6 patients with DLTs in the first cycle (28 days) of treatment. If any patients in the first 6 of each treatment arm withdraw from the study without a DLT event prior to completing the first cycle of treatment, they will be replaced for the assessment of DLT rate. This will allow for early identification of significant toxicities and early stoppage in potentially toxic arms. If 2 or more out of 6 patients with DLTs in the first cycle of treatment, then additional 6 patients will enroll at a lower dose level. If no more than 1 out of the additional 6 patients treated with lower dose level experienced DLTs, this treatment combination will be considered as safe and continue to enroll to a total of 30 patients (arm B), 24 (arms C-D) or 15 patients (arms E-F). If 2 or more out of these 6 additional patients experienced DLTs, then this arm will be halted.

Arm F will be closed at this time to further enrollment due to lack of clinical efficacy and competing options of higher priority at our institution.

Futility Monitoring for Arms B-F

The primary endpoint of Arm B-F is the achievement of composite complete response (CRc) within 3 months of therapy initiation in patients with RR AML. The method of Thall, Simon and Estey (1995) will be used to monitor efficacy and safety. After the lead-in, shiny applications were used to generate the operating characteristics for toxicity and futility monitoring, respectively (<http://qcprlshinypyro.mdanderson.edu/postprobtoxicity/>, <http://qcprlshinypyro.mdanderson.edu/postprobfutility/>).

The historical data suggested a composite complete response (CRc) rate of 30% in patients with R/R AML with a variety of different therapies^{4,110,119-122}, and a target response rate is 45%. The study arm will be stopped early if the data suggest that:

$$\Pr(P_E > P_H + 0.15 \mid \text{data}) < 0.05,$$

where P_E and P_H are the CRc rates for experimental and historical treatment, respectively. That is, if at any time during the study we determine that there is less than 5% chance that the CRc rate improves over historical rate by more than 15%, the arm will be stopped due to futility. P_E is assumed to follow a prior of Beta (0.6, 1.4). The futility monitoring will be conducted starting from the 10th patient in cohort size of 5 patients except the last cohorts with less than 5 patients. The design parameters are set the same for arms B-F, while separate futility monitoring analyses were conducted to accommodate different numbers of patients among these arms.

Arm F will be closed at this time to further enrollment due to lack of clinical efficacy and competing options of higher priority at our institution.

Arm B

The stopping boundaries for efficacy based on these assumptions and monitoring conditions are provided in Table 14. The operating characteristics are summarized in Table 15.

If the study arm is not stopped early and 24 patients have been treated and evaluated in the study arm, assuming 8 of the 24 patients achieve CRc under the combination treatment, then the 95% credible interval for CRc rate will be (0.17, 0.52).

Table 14. Stopping boundaries for futility monitoring in Arm B

# of patients evaluated for response	Stop the arm if # of patients with response is less than or equal to:
10	0-2
15	0-3
20	0-5
24	Always stop with this many patients

Table 15. Operating characteristics for futility monitoring in Arm B-D

True response rate	Prob(stop the arm early)	Average sample size
0.15	0.952	11.7
0.25	0.702	15.6
0.30	0.525	17.8
0.35	0.357	19.8
0.45	0.126	22.5
0.55	0.031	23.6
0.65	0.005	23.9

Arm C-D

The stopping boundaries for efficacy based on these assumptions and monitoring conditions are provided in Table 16. The operating characteristics are summarized in Table 17.

If the study arm is not stopped early and 18 patients have been treated and evaluated in the study arm, assuming 6 of the 18 patients achieve CRc under the combination treatment, then the 95% credible interval for CRc rate will be (0.15, 0.54).

Table 16. Stopping boundaries for futility monitoring in Arm C-D

# of patients evaluated for response	Stop the arm if # of patients with response is less than or equal to:
10	0-2
15	0-3
18	Always stop with this many patients

Table 17. Operating characteristics for futility monitoring in Arm C-D

True response rate	Prob(stop the arm early)	Average sample size
0.15	0.878	11.3
0.25	0.585	13.6
0.30	0.428	14.8
0.35	0.291	15.8
0.45	0.108	17.2
0.55	0.029	17.8
0.65	0.005	18.0

Arm E-F

The stopping boundaries for efficacy based on the same assumptions and monitoring conditions are provided in Table 18. The operating characteristics are summarized in Table 19. If the study arm is not stopped early and 15 patients have been treated and evaluated in the study arm, assuming 5 of the 15 patients achieve CRc under the combination treatment, then the 95% credible interval for CRc rate will be (0.13, 0.56).

Arm F will be closed at this time to further enrollment due to lack of clinical efficacy and competing options of higher priority at our institution.

Table 18. Stopping boundaries for futility monitoring in Arm E-F

# of patients evaluated for response	Stop the arm if # of patients with response is less than or equal to:
10	0-2
15	Always stop with this many patients

Table 19. Operating characteristics for futility monitoring in Arm E-F

True response rate	Prob(stop the arm early)	Average sample size
0.15	0.820	10.9
0.25	0.526	12.4
0.30	0.383	13.1
0.35	0.262	13.7
0.45	0.100	14.5
0.55	0.027	14.9
0.65	0.005	15.0

Toxicity Monitoring for Arm B-F

The method of Thall, Simon and Estey will be used for toxicity monitoring for this study. Denote the probability of DLT by P_T . We assume as a priori, $P_T \sim \text{beta}(0.3, 1.7)$. Our stopping rule is: if 2 or more out of 6 patients with DLTs in the first cycle of treatment, then additional 6 patients will enroll at a lower dose level. If 2 or more out of these 6 additional patients experienced DLTs, then this arm will be halted. Otherwise, we will stop the arm if $\Pr(P_T > 0.15 | \text{data}) > 0.80$. That is, we will stop the arm for new patient enrollment if at any time during the study, we determine that there is more than 80%

chance that the toxicity rate is more than 15%. Again, the design parameters are set the same for arms B-F, while separate toxicity monitoring analyses were conducted to accommodate different numbers of patients among these arms.

Arm F will be closed at this time to further enrollment due to lack of clinical efficacy and competing options of higher priority at our institution.

Arm B

The toxicity stopping rule will be applied starting from the 6th patient, and then in cohort size of 3. Stopping boundaries corresponding to the above stopping rule are listed in Table 18. The operating characteristics are summarized in Table 19.

Table 18. Early stopping boundaries for toxicity monitoring arm B

# of patients (in cohort size of 3, starting from the 6 th patient)	Stop the arm if there are this many patients with toxicities:
6	2-6
9	3-9
12	4-12
15	4-15
18	5-18
21	5-21
24	Always stop

Table 19. Operating characteristics for toxicity monitoring arm B

True toxicity rate	Prob(stop the arm early)	Average sample size
0.10	0.163	21.4
0.15	0.342	19.0
0.20	0.555	16.0
0.25	0.731	13.4
0.30	0.856	11.0
0.40	0.976	8.0

Arm C-D

The toxicity stopping rule will be applied starting from the 6th patient, and then in cohort size of 3. Stopping boundaries corresponding to the above stopping rule are listed in Table 18. The operating characteristics are summarized in Table 19.

Table 20. Early stopping boundaries for toxicity monitoring arm C-D

# of patients (in cohort size of 3, starting from the 6 th patient)	Stop the arm if there are this many patients with toxicities:
6	2-6
9	3-9
12	4-12

15	4-15
18	Always stop

Table 21. Operating characteristics for toxicity monitoring arm C-D

True toxicity rate	Prob(stop the arm early)	Average sample size
0.10	0.137	16.5
0.15	0.290	15.0
0.20	0.485	13.1
0.25	0.653	11.4
0.30	0.771	10.1
0.40	0.936	7.8

Arm E - F

The toxicity stopping rule will be applied starting from the 6th patient, and then in cohort size of 3. Stopping boundaries corresponding to the above stopping rule are listed in Table 22. The operating characteristics are summarized in Table 23.

Arm F will be closed at this time to further enrollment due to lack of clinical efficacy and competing options of higher priority at our institution.

Table 22. Early stopping boundaries for toxicity monitoring arm E-F

# of patients (in cohort size of 3, starting from the 6 th patient)	Stop the arm if there are this many patients with toxicities:
6	2-6
9	3-9
12	4-12
15	Always stop

Table 23. Operating characteristics for toxicity monitoring arm E-F

True toxicity rate	Prob(stop the arm early)	Average sample size
0.10	0.122	13.9
0.15	0.264	12.8
0.20	0.410	11.6
0.25	0.562	10.3
0.30	0.685	9.3
0.40	0.874	7.6

Statistical Analysis Plan

Demographic/clinical characteristics and safety data will be summarized using descriptive statistics such as mean, standard deviation, median and range. The composite complete response (CRc) rates, partial response (PR), hematologic improvement (HI) rate, 4-week and 8-week mortality will be estimated along with the

95% credible intervals. Kaplan-Meier method will be used to estimate the relapse-free survival (RFS), morphologic leukemia free survival (MLFS), time to next therapy (TNT) and overall survival (OS). The two-sided log-rank tests will be used to assess the differences of time to events between groups. Cox proportional hazards regression model will be used to determine associations between MRD and OS.

All patients who received at least one dose of study drug will be included in the intent-to-treat analysis for efficacy and safety. We will follow standard reporting guidelines for adverse events. Safety data will be summarized by category, severity and frequency. Paired t-tests will be used to determine the immunological and molecular changes in the peripheral blood and bone marrow from baseline to the predefined time-points on-therapy.

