5.2 Schedule

The Investigator is responsible for completing Safety/Efficacy Monitoring summary reports and submitting to the IND office Medical Affairs and Safety Group for review and approval. These should be submitted as follows:

- Arm A:
Every 4 evaluable subjects, after completion of 28 days of study treatment. Study enrollment of this arm must be held until IND approval is obtained.
- Lead-In and Phase II for Arms B to F:
 - Safety monitoring
 - Lead-in: After the first 6 evaluable subjects, per arm, complete 2 cycles of therapy and every 3 evaluable subjects, per arm, thereafter. Enrollment must be halted for that individual arm while the first 6 patients of that arm are evaluated for safety (i.e. after all patients have received 2 cycles of therapy, or been followed for at least 56 days from the start of treatment or at least 56 days from the first dose of venetoclax in the venetoclax containing arms B and D).
 - Phase II: After the first 6 evaluable subjects, per arm, complete 2 cycles of therapy and every 3 evaluable subjects, per arm, thereafter.
 - Futility monitoring
 - Futility summary will be submitted after the first 10 evaluable subjects, per arm, complete 3 cycles of therapy and every 5 evaluable subjects, per arm, thereafter.

The dosing calculations should be based on the body weight. All doses should be rounded to the nearest milligram for all agents. There will be no dose reductions (only interruptions when indicated) allowed for avelumab and PF-04518600 on this trial.

Patients will be treated according to the following schedules that are specific to each arm:

(A) Arm A (PF-04518600 alone in RR AML) (6 patient dose-finding cohort):

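### The average sample sizes for futility monitoring (Tables 15 and 17) count no patient enrolled while outcomes are pending, so they are minimum values unless enrolment pauses at each look

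*Combined protocol and SAP*

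**What the plan says.** The primary endpoint for Arms B-F is "achievement of composite complete response (CRc) within 3 months of therapy initiation in patients with RR AML" (Section 11.0). For the futility rule, the same section says "The futility monitoring will be conducted starting from the 10th patient in cohort size of 5 patients". The tables place looks at 10, 15 and 20 patients with a maximum of 24 (Arm B) and at 10 and 15 with a maximum of 18 (Arms C-D). Neither an accrual rate nor an outcome delay is given with Tables 15 and 17.

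Section 5.2 sets the timing: "Futility summary will be submitted after the first 10 evaluable subjects, per arm, complete 3 cycles of therapy and every 5 evaluable subjects" thereafter. Section 5.3 defines a cycle as 28 days, give or take 4.

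Enrolment holds are written elsewhere. For the lead-in of Arms B-F, Section 11.0 says "Enrollment must be halted while the first 6 patients in each treatment arm are evaluated for safety", and Sections 3.3, 3.4 and 5.2 say the same. Section 5.2 also holds Arm A until the IND office approves. The futility item in Section 5.2 contains no hold.

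**The concern.** A look that needs the 3-month outcome of its last patient takes place about 84 days after that patient starts. Without a hold, further patients enter the arm in that time and are treated even if the look then closes it. The printed averages leave them out.

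Section 2.4 justifies the design partly by early closure of arms that perform poorly. Average sample size at low response rates is the figure that supports this, and it is where the omission is largest.

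A second problem needs no accrual assumption. Section 5.2 waits for evaluable subjects who complete 3 cycles. Sections 5.4.8 and 11.0 include every patient with at least one dose in the efficacy analysis, and Section 2.1 gives survival of 1 to 4 months with standard salvage therapy. A patient who dies or leaves for progression in cycle 1 never completes 3 cycles, although the outcome is known. Section 2.8 already describes 2 of the 5 Arm F patients as not evaluable for response because they died before assessment.

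**Working it through.** **Inputs.** From Section 11.0: prior Beta(0.6, 1.4); stop if the posterior probability that the CRc rate exceeds 0.30 + 0.15 = 0.45 is below 0.05; looks and maxima as above. From Sections 5.2 and 5.3: delay of 3 × 28 = 84 days, taken as 3 months. Accrual per arm is not stated, so 0.5, 1, 2 and 3 patients per month are assumptions.

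**Step 1: boundaries.** With x responders in n patients the posterior is Beta(0.6 + x, 1.4 + n − x). The probability of exceeding 0.45 is 0.0376 at 2/10 and 0.130 at 3/10; 0.0165 at 3/15 and 0.0567 at 4/15; 0.0255 at 5/20 and 0.0687 at 6/20. The printed boundaries (2, 3 and 5) are confirmed.

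**Step 2: printed averages.** Let s_n be the exact binomial probability of first stopping at look n. Then average = Σ s_n × n + (1 − Σ s_n) × N.

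- At a true 15%: s_10 = 0.8202, s_15 = 0.0576, s_20 = 0.0739.
  - Arm B: 0.8202×10 + 0.0576×15 + 0.0739×20 + 0.0483×24 = 11.70 (stated 11.7).
  - Arms C-D: 0.8202×10 + 0.0576×15 + 0.1222×18 = 11.27 (stated 11.3).
- At a true 30%: s_10 = 0.3828, s_15 = 0.0448, s_20 = 0.0974.
  - Arm B: 3.828 + 0.672 + 1.948 + 0.4750×24 = 17.848 (stated 17.8).
  - Arms C-D: 3.828 + 0.672 + 0.5724×18 = 14.80 (stated 14.8).

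All 14 rows of Tables 15 and 17 reproduce to rounding in this way. The printed averages therefore assume either that outcomes are known at once or that enrolment pauses at every look.

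**Step 3: add the delay.** Keep the same s_n, but count min(N, n + k) patients in a stopped arm, where k = 3 × monthly accrual rounded down (1, 3, 6, 9). Example, Arm B, 15%, 2 per month: 0.8202×16 + 0.0576×21 + 0.0739×24 + 0.0483×24 = 17.27.

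| Arm, maximum | True CRc | Stated | 0.5/month | 1/month | 2/month | 3/month |
|---|---|---|---|---|---|---|
| B, 24 | 15% | 11.7 | 12.7 | 14.6 | 17.3 | 19.9 |
| B, 24 | 30% | 17.8 | 18.4 | 19.4 | 20.8 | 22.1 |
| B, 24 | 45% | 22.5 | 22.6 | 22.8 | 23.2 | 23.5 |
| C-D, 18 | 15% | 11.3 | 12.1 | 13.9 | 16.4 | 18.0 |
| C-D, 18 | 30% | 14.8 | 15.2 | 16.1 | 17.2 | 18.0 |
| C-D, 18 | 45% | 17.2 | 17.3 | 17.5 | 17.8 | 18.0 |

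At 45% the rise cannot exceed 24 − 22.46 = 1.5 patients in Arm B or 18 − 17.18 = 0.8 in Arms C-D, whatever the accrual. A simulation with random (Poisson) accrual and an 84-day delay agrees: Arm B at 30% averages 19.3 at 1 per month and 20.6 at 2 per month.

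**Step 4: who is left at the late looks.** This depends on the arm maximum. Planned enrolment is 30 in Arm B and 24 in each of Arms C-D, in both cases 6 above the table maximum. That gap equals the lead-in, yet Section 5.2 counts the first 10 evaluable subjects per arm without excluding lead-in patients.

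- Arms C-D, look at 15, 1 per month: 3 more enter. With a maximum of 18, 18 − 18 = 0 are spared; with 24, 24 − 18 = 6 are spared.
- Arms C-D, look at 10, 3 per month: 9 more enter. With a maximum of 18 none is spared; with 24 the arm closes at 19 and spares 5.
- Arm B, look at 20: with a maximum of 24, 4 remain, and none is spared from 4/3 = 1.33 per month. With 30, 10 remain.

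**The case against.** Nothing printed is miscalculated: boundaries, stopping probabilities and averages all reproduce. A reader might infer an arithmetic error, but the documents show only an unstated assumption.

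A reader might also infer that enrolment certainly continues during a futility look. No sentence says so. Section 5.2 sends the monitoring summaries to the IND office for review and approval, and Section 3.3 requires approval before accrual goes beyond each set of 6 patients. The Section 3.3 text concerns safety cohorts, so it does not settle the matter, but a pause at futility looks is not excluded. If there is one, the tables are exact. This objection stands, and it makes the conclusion conditional.

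A third tempting inference is that the late looks, or all looks in Arms C-D, save no one. That needs the table maxima of 18 and 24 together with fast enough accrual. With planned enrolment of 24 and 30 it fails, as step 4 shows.

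Slow accrual is plausible. Section 3.5 has Arm F opening alongside Arm A. Arm A had 4 treated by 4 June 2019 and Arm F had 5 by 18 March 2020. If Arm F was open by June 2019 (an assumption), that is at most about 5 / 9.5 = 0.5 per month. Arms B-D may differ. At that rate the shift is about one patient. A true 15% is also half the historical 30%, and nearer the target the shift is small.

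Finally, counting patients as soon as outcomes become known could over-represent early deaths or early responders. That is a fair warning about the remedy, and the fix below allows for it.

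**Conclusion.** The point holds in conditional form. Unless enrolment pauses at each futility look, the averages in Tables 15 and 17 are minimum values. The understatement at a true 15% runs from about 1 patient at 0.5 per month to 19.9 − 11.7 = 8.2 (Arm B) or 18.0 − 11.3 = 6.7 (Arms C-D) at 3 per month. At 30% it runs from about half a patient to 4.3 or 3.2. These sizes rest on the assumed accrual, a 3-month delay and the table maxima. The stopping rule itself and its crossing probabilities are sound and unaffected. How many patients the late looks can spare cannot be stated until the plan says whether lead-in patients count.

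The trigger in Section 5.2 needs repair whatever the accrual. One might infer that early deaths will be dropped from the futility count. The documents do not say that, and Section 5.4.8 points the other way, but the wording leaves it open. This is a minor point of reporting and wording, not a flaw in the decision rule.

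**What to change.** 1. In Section 11.0, state whether enrolment pauses at futility looks. If it does not, either label the averages in Tables 15 and 17 as excluding patients enrolled while outcomes are pending (minimum values), or recompute them at the expected accrual rate and the actual arm maximum, saying whether the 6 lead-in patients count.
2. In Section 5.2, base each look on the first 10, 15 or 20 treated patients in enrolment order. Hold it once each of them has reached CRc, death, off-study for progression, or 3 months, and count those without CRc as non-responders. This replaces waiting for subjects who complete 3 cycles. Fixing the set by enrolment order keeps early-known outcomes from being over-represented and keeps the printed stopping probabilities valid.

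The cost is a recalculation and a few sentences. The stated averages may become less favourable. No enrolment hold is required. The gain in time from item 2 may be small, because a late-enrolled patient who is alive without response must still reach 3 months; the main gain is an unambiguous count.
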